1.3 Research Design and Methods

We will conduct a randomized clinical trial enrolling eligible participants who are determined to be SARS-CoV-2-positive (e.g., via Rutgers Corona Cohort [RCC] study, hospital or other screening programs) who volunteer for the study. Specifically, we will enroll 70 participants whose test has been performed within the past 7 days who are either asymptomatic or mildly symptomatic at baseline. Mild COVID-19 symptoms include new cough, sore throat, fever, myalgias, new vomiting or diarrheaor change in smell or taste. Illness requiring hospitalization, or those who present with hypoxia (PO2<92%) or shortness of breath at time of enrollment will be classified as significantly symptomatic and excluded from study participation. People who are allergic or intolerant to NTZ, RBV or HCQ will be excluded. We will randomly allocate participants stratified by presence of mild symptoms to 1) NTZ, RBV and HCQ or 2) placebo. Treatment with the investigational agents or placebo will continue for 5 days. Viral load will be assessed at baseline (day 0) as well as at days 3, 6, and 10 to monitor response to antiviral treatment. Immune status will be determined by antibody testing of blood collected at baseline and day 28.

Prior to initiating enrollment, we will prepare two randomization tables for treatment assignment using permuted blocks of six which will be provided to the research pharmacist. One table will be used for participants without symptoms and the other will be used for those with mild symptoms. The pharmacist will prepare kits containing the 5-day supply of study medications (investigational drugs/placebo) which will be sequentially numbered in accordance with the randomization tables. The contents of each kit (investigation drugs/placebo) will be indistinguishable. Study staff will establish symptom status at the baseline visit, and per pharmacy order, provide the participant the next numbered medication kit in the participant's stratum (no symptoms/mild symptoms). The study investigators, staff interacting with the participants are all masked to treatment assignment

A. Research Procedures

- 1. Study Procedures:
 - Day 0/1 Screening/Baseline Visit (in person)
 - Pre-screen via online screening form to confirm eligibility
 - Obtain informed consent for trial enrollment
 - Medical history
 - Medication history
 - Document symptoms (if any)

- o Take temperature, PO2, Pulse
- Q-T interval assessment

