 - Arm 1: NTZ 1000 mg (2 x 250 mg tablets BID for day one) and then 1000 mg (2 x 250 mg tablets BID for 4 days) RBV 1200 mg (3 x 200 mg capsules BID day one) and then RBV 800 mg (2 x 200mg capsules BID for 4 days) HCQ 800 mg (2 x 200 mg tablets bid day one) and then HCQ 400 mg (1 x 200 mg tablet BID for 4 days)
 - Arm 2: Placebo for NTZ (2 tablets BID for day one and then 2 tablets BID for 4 days) Placebo for RBV (3 capsules BID day one and then 2 capsules BID for 4 days) Placebo for HCQ (2 tablets bid day one and then 1 tablet BID for 4 days)

Hydroxychloroquine sulfate (HCQ)

One hydroxychloroquine sulfate tablet contains 200 mg of hydroxychloroquine sulfate, which is the equivalent to 155 mg base.

Ribavirin (RBV)

One ribavirin capsule contains 200 mg of ribavirin.

Nitazoxanide (NTZ)

One nitazoxanide tablet contains 500 mg of nitazoxanide.

Take all tablets/capsules with a meal or a glass of milk.

All study drugs should be stored at room temperature 20°-25° (68°-77 °F).

Concomitant Medications & Supportive Guidelines

Study participants can receive full supportive care therapies concomitantly during the study. We will advise rest, fluids, hot/ showers/baths. We will recommend NO antipyretics since they make infections worse by interfering with the generation of fever--which is considered beneficial until it reaches 102 degrees F.

B. Participant Enrollment

We will identify asymptomatic or mildly symptomatic participants who test positive for SARS-CoV-2 from the Rutgers Coronavirus Cohort (RCC) and hospital screening programs, or from the community through advertisements at our medical center, university, and in local publications. The recruiting materials will direct the potential participants to online materials that include information about the trial, consent forms, and a screener questionnaire to assess eligibility. If eligible for the trial, we will answer any questions and provide as much time as needed to review all study materials. The participant may then electronically sign the consent or, as an alternative, wait until the initial visit to re-review and sign the consent. The consenting process will be primarily performed remotely to protect research personnel.

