QT interval will be measured on an ongoing basis through day 10 via the Zio AT mobile cardiac telemetry device describe in section 4.7 E. If the corrected QT - QTc interval increases from baseline of > 60msec or QT > 500 msec, the medications, if still being taken, will discontinued at that time. Participant QTc intervals will be monitored every 6 hours until the interval returns to baseline. If a serous arrhythmia is detected during the continuous monitoring, the study cardiologist and participant will be promptly contacted, and the participant will be directed to seek medical treatment as appropriate.

C. Study Safety Assessments

The Principal Investigator is responsible for ensuring that all staff involved in the study are familiar with the content of this section.

- 1. Definitions:
 - Adverse Events:

An adverse event is the development of an undesirable medical condition or the deterioration of a pre-existing medical condition following or during exposure to a pharmaceutical product, whether considered causally related to the product. An undesirable medical condition can be symptoms (e.g., nausea, chest pain), signs (e.g., tachycardia, enlarged liver), or the abnormal results of an investigation (e.g., laboratory findings, electrocardiogram). In clinical studies, an AE can include an undesirable medical condition occurring at any time, including run-in or washout periods, even if no study treatment has been administered. The term AE is used to include both serious and non-serious AEs.

• Serious Adverse Events:

A serious adverse event is an AE occurring during any study phase (i.e., screening, runin, treatment, wash-out, follow-up), at any dose of the study drugs that fulfills one or more of the following criteria:

- Results in death
- Is immediately life-threatening
- Requires in-patient hospitalization or prolongation of existing hospitalization
- Results in persistent or significant disability or incapacity

- Is a congenital abnormality or birth defect
- Is an important medical event that may jeopardize the patient or may require medical intervention to prevent one of the outcomes listed above.
- The causality of SAEs (their relationship to all study treatment/procedures) will be assessed by the investigator(s) and communicated to the FDA via MedWatch form, if applicable.
- 2. Recording of Adverse Events

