Cardiac Effects, including Cardiomyopathy and QT prolongation: Post-marketing cases of life-threatening and fatal cardiomyopathy have been reported with use of hydroxychloroquine sulfate as well as with use of chloroquine. Hydroxychloroquine sulfate prolongs the QT interval. Ventricular arrhythmias and torsades de pointes have been reported in patients taking hydroxychloroquine sulfate (see OVERDOSAGE). Therefore, hydroxychloroquine sulfate should not be administered with other drugs that have the potential to prolong the QT interval.

Worsening of psoriasis and porphyria

Proximal Myopathy and Neuropathy

Neuropsychiatric events, including suicidality

Hypoglycemia: Hydroxychloroquine sulfate has been shown to cause severe hypoglycemia including loss of consciousness that could be life threatening in patients treated with or without antidiabetic medications

General precautions: General: Use with caution in patients with gastrointestinal, neurological, or blood disorders, and in those with a sensitivity to quinine.

Hepatic/Renal Disease: Antimalarial compounds should be used with caution in patients with hepatic disease or alcoholism or in conjunction with known hepatotoxic drugs. A reduction in dosage may be necessary in patients with hepatic or renal disease, as well as in those taking medicines known to affect these organs.

Hematologic Effects/Laboratory Tests: Antimalarial compounds should be used with caution in patients with hepatic disease or alcoholism or in conjunction with known hepatotoxic drugs. Periodic blood cell counts should be performed if patients are given prolonged therapy.

Hydroxychloroquine sulfate should be administered with caution in patients having glucose-6-phosphate dehydrogenase (G-6-PD) deficiency.

Dermatologic Effects: Dermatologic reactions to hydroxychloroquine sulfate may occur and, therefore, proper care should be exercised when it is administered to any patient receiving a drug with a significant tendency to produce dermatitis.

Drug Interactions (include but not limited to): Digoxin, Insulin or antidiabetic drugs, Drugs that prolong QT interval and other arrhythmogenic drugs, Mefloquine and other drugs known to lower the convulsive threshold, Antiepileptics, Methotrexate, Cyclosporin, Praziquantel, Antacids and kaolin, Cimetidine, Ampicillin.

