The participant will then come to the study location at [name] to complete final screening for the trial eligibility. P02 will be measured and 6 lead portable electrocardiogram will be performed; if PO2<92% or QT interval is QTc interval > 450 mSEC the participant will be excluded. Females of childbearing potential will have a urine test to confirm that they are not pregnant.

Inclusion Criteria

- 1. Documented SARS-CoV-2 infection by qPCR assay without symptoms or with mild symptoms consistent with COVID-19 performed within the past 7 days
- 2. Age ≥21

Exclusion Criteria

- 1. COVID-19 symptoms requiring hospitalization
- 2. PO2 < 92%
- 3. Short of breath at time of enrollment
- 4. Retinal eye disease
- 5. Known glucose-6 phosphate dehydrogenase (G-6-PD) deficiency
- 6. Known chronic kidney disease, stage 5 or receiving dialysis
- 7. Current use of:
 - Class 3 AAD (amiodarone, dronaderone, dofetilide, sotalol)
 - Class 1A AAD (procainamide, quinidine, disopyramide)
 - Flecainide
 - SSRI: citalopram (Celexa), Escitalopram (Lexapro)
 - chlorpromazine
 - Cilostazol (Pletal)
 - Donepezil (Aricept)
 - Droperidol
 - Fluoconazole
 - Methadone
 - Ondansetron (Zofran)
 - Thioridazine
 - Macrolides (clarithromycin, erythromycin)
 - Fluroquinolones (ciprofloxacin, levofloxacin, moxifloxacin)
 - Tamoxifen citrate
- 8. Pregnancy or women who are breast feeding
- 9. Inability to tolerate oral medications
- 10. Allergy or prior adverse reaction to either hydroxychloroquine sulfate, ribavirin, or nitazoxanide
- 11. Allergy to adhesives
- 12. QTc interval > 450 mSEC for men and women
- 13. History of Torsade de Pointes VT or prior cardiac arrest or congenital long QT interval
- 14. Non-English-speaking

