4.6 Economic Burden and/or Compensation for Participants

A. Expenses

The study drugs will be provided at no charge. At the initial visit we will provide each participant with a Zio AT mobile cardiac telemetry device. Participants will return the device at their day 28 visit. Study participants will not be charged for the cost of any research procedures which are conducted as part of this study. Participants and/or their insurance carriers (or Charity Care in the absence of insurance) will be expected to pay for the standard of care costs related to COVID-19 treatment and follow-up and for any other medical treatment (e.g., drug reactions) they require.

B. Compensation/Incentives

Participants will receive a ClinCard at the initial study visit, which will be preloaded with money to pay for that day's parking. On the day 14 and 28 day visits, we will add money to that card to cover the parking costs on those days as well.

We will add additional money to the card at the final (day 28) study visit (maximum amount \$50). The amount of they receive will be based on completion of the study tasks: \$25 for completing all of the self-collected specimens (days 3, 6, & 10) and \$25 for completing both the day 24 and day 28 (final) study visit and returning ZioAT monitoring device.

Participants will also keep the thermometer and the pulse oximeter provided at the initial study visit,

C. Compensation Documentation

None

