Uncommon: ≥ 0.1 and < 1 %: Maculopathies, which may be irreversible. Retinopathy with changes in pigmentation and visual field defects (see Warnings and Precautions, Ophthalmologic). In its early form it appears reversible upon discontinuation of the drug. If allowed to develop however, there may be a risk of progression even after treatment withdrawal. Patients with retinal changes may be asymptomatic initially, or may have scotomatous vision with paracentral, pericentral ring types, temporal scotomas, abnormal color visions, reduction in visual acuity, night blindness, difficulty reading and skipping words. Corneal changes including edema and opacities. They are either symptomless or may cause disturbances such as halos around lights especially at night, blurring of vision, vision disturbances, or photophobia. They may be transient or are reversible upon discontinuation of therapy (see Warnings and Precautions, Ophthalmologic). *Not known*: Macular degeneration, which may be irreversible.

Gastrointestinal disorders

Very common: \geq 10 %: Abdominal pain, nausea. Common: Diarrhea, vomiting. These symptoms usually resolve immediately upon reducing the dose or upon stopping the treatment.

• Hepatobiliary disorders

Uncommon: ≥ 0.1 and < 1 %: Abnormal liver function tests. Not known: Fulminant hepatic failure (see Warnings and Precautions, Hepatic/Biliary/Pancreatic).

Immune system disorders

Not known: Urticaria, angioedema, bronchospasm.

• Metabolism and nutrition disorders

Common: \geq 1 and <10 %: Anorexia (usually resolves immediately upon reducing the dose or upon stopping the treatment). Not known: hypoglycemia (see Warnings and Precautions, Endocrine and Metabolism). Hydroxychloroquine may exacerbate porphyria (see Warnings and Precautions, General).

• Musculoskeletal and connective tissue disorders

Uncommon: ≥ 0.1 and < 1 %: Sensori motor disorders. Not known: Skeletal muscle palsies or skeletal muscle myopathy or neuromyopathy leading to progressive weakness and atrophy of proximal muscle groups. Depression of tendon reflexes, abnormal results of nerve conduction tests. Myopathy may be reversible after drug discontinuation, but recovery may take many months (see Warnings and Precautions, Musculoskeletal).

• Nervous system disorders

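### The warning against combining HCQ with other QT-prolonging drugs becomes a study rule only at entry; it is not carried into the on-study medication rules, the days after dosing up to day 10, or the stopping rule

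*Combined protocol and SAP*

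**What the plan says.** The HCQ warnings in section 1.7 state that "hydroxychloroquine sulfate should not be administered with other drugs that have the potential to prolong the QT interval". The wording is general and not limited to entry.

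The eligibility rule is exclusion item 7 in section 4.1. It opens with "Current use of" and lists, among others, class 1A and class 3 antiarrhythmics, citalopram and escitalopram, ondansetron, methadone, macrolides and fluoroquinolones.

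The rule after entry is the paragraph on concomitant medications and supportive guidelines in section 1.3 (Treatment Plan): "Study participants can receive full supportive care therapies concomitantly during the study". It goes on to rest, fluids and warm bathing, and advises against antipyretics. It names no QT-prolonging drug.

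QTc is followed by patch telemetry through day 10 (sections 1.3 B and 4.7 E). If the interval rises more than 60 msec from baseline, or QT exceeds 500 msec, "the medications, if still being taken, will discontinued at that time", and QTc is then checked every 6 hours until it returns to baseline.

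**The concern.** Item 7 screens out people already on a listed drug. It does not address someone who starts one on day 2 or day 7.

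The need for such a drug is foreseeable. Section 1.3 says "Mild COVID-19 symptoms include new cough, sore throat, fever, myalgias, new vomiting or diarrheaor change in smell or taste". Section 4.7 puts "Abdominal pain, nausea" in its very common category for HCQ (10% or more). Ondansetron and two antibiotic classes are on the item 7 list.

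The likely route is an outside prescriber. Participants are at home, with no scheduled in-person visit between baseline and day 14. Under section 4.6, participants or their insurers "will be expected to pay for the standard of care costs related to COVID-19 treatment and follow-up and for any other medical treatment", with drug reactions given as an example.

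The outcome to avoid is a ventricular arrhythmia such as torsades de pointes, which section 1.7 names. Section 1.2 cites 40 reports of sudden or QT-related death after any antimalarial, 16 of them with another potentially QT-prolonging medicine. These are spontaneous reports across all antimalarials, so they show the mechanism and give no rate.

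**Working it through.** The plan gives no figure on this point to reproduce. The check sets the provisions side by side, then adds two small calculations for scale.

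**Coverage by period**

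| Period | Rule on QT-prolonging drugs in the supplied text |
|---|---|
| Entry | Item 7 exclusion; QTc above 450 msec excluded; prior torsades, cardiac arrest or congenital long QT excluded |
| Dosing, days 1 to 5 | General warning in section 1.7; nothing in the concomitant-medication paragraph |
| After dosing, to day 10 | QTc monitoring only; no wording on new drugs |

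**What the stopping rule can do.** The drug action it specifies is to stop study medication. During dosing that removes one of two contributors. On days 6 to 10 dosing is over, so the rule leaves no drug to stop, although an added QT-prolonging drug would be a modifiable cause.

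**Is HCQ still present on days 6 to 10?** Section 1.7 gives a blood half-life of 22.4 days. Assuming single-phase elimination at that half-life, the fraction remaining 5 days after the last dose is 2^(-5/22.4) = 0.857, or about 86%. Exposure therefore continues through the monitoring period.

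**Would the team hear of a new drug in time?**
- Concomitant medications and standard-of-care COVID-19 treatments are data points, with eCRFs due within 72 hours of a time point (section 1.3 D). No restriction or review is attached to them.
- The calls on days 3, 6 and 10 cover procedures, specimens, adverse events, medical status and, on days 3 and 6, dosing (sections 1.3 B and 1.9 A). The follow-up questionnaires cover symptoms, reactions to study drug and household health. No described item asks about new medicines.
- Grade 1 and 2 adverse events need not be recorded (section 1.3 C), so milder nausea that leads to an antiemetic need not appear.
- Record abstraction is retrospective and leaves out participants who stay asymptomatic and unrelated conditions (section 1.9 B).

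**Scale of the antiemetic route**
- Inputs: 35 participants on HCQ (section 1.5); nausea at 10%, the lower bound of the very common category (section 4.7).
- Expected number with nausea: 0.10 × 35 = 3.5.
- Let s be the share of these given a listed antiemetic. The documents give no value, so s is an assumption.
- Expected co-exposed = 35 × 0.10 × s. Chance of at least one = 1 − (1 − 0.10s)^35.

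| s | Expected co-exposed | Chance of at least one |
|---|---|---|
| 5% | 0.175 | 1 − 0.995^35 = 16% |
| 10% | 0.35 | 1 − 0.99^35 = 30% |
| 30% | 1.05 | 1 − 0.97^35 = 66% |

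This counts co-exposure, not harm, and covers one route only.

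**The case against.** The strongest reply is that the protocol does speak to co-administration. A reader might infer that nothing in it bars starting a QT-prolonging drug while HCQ is being taken. The documents do not support that: the section 1.7 warning is part of the protocol body and its wording covers the dosing days. What stands is narrower. The warning is label text that gives participants and outside prescribers no instruction, specifies no action if such a drug is started, and does not explicitly reach the days after dosing.

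A reader might also take the supportive-care sentence as permission to start any drug. Its context is rest, fluids and bathing, so that is too much. The point is that it omits the list, not that it overrides the warning.

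The safeguards are substantial: the entry QTc limit and history exclusions, a reading 2 hours after the first dose, twice-daily QTc measured by the electrophysiology team, continuous telemetry with immediate notification of ventricular runs, and the stopping thresholds. A cardiology team that saw prolongation might well ask about other drugs unprompted. All of this makes serious harm unlikely. It still works after co-exposure has happened.

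Finally, consent pages, call scripts, questionnaires and the data capture plan were not supplied. An instruction to tell other doctors about the trial could sit there, so absence can be stated only for the supplied text.

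**Conclusion.** The concern holds as a modest patient-safety gap. The plan repeats the hazard in its drug information and acts on it at entry, but does not carry it into the on-study medication rules, the period from the end of dosing to day 10, or the stopping rule. Followed as written, the operating rules leave room for a co-exposure that the protocol itself warns against.

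The size is small: probably none to one participant through the antiemetic route, under close QTc monitoring. That rests on an unsourced 5% to 30% prescribing share and on a label nausea rate drawn mostly from longer use than the 5 days here. Overall co-exposure frequency cannot be estimated from the documents.

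A reader might infer that new co-medication confounds the comparison between arms. The documents do not support this: the groups are randomised, masked and analysed as randomised, and the primary endpoint is viral load decline. Neither that endpoint nor power is affected.

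Whether the macrolide entry in item 7, which names clarithromycin and erythromycin, also covers azithromycin is a minor clarification for the clinical team and is not needed for this conclusion.

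**What to change.** 1. In the concomitant-medication paragraph of section 1.3, state that the QT-prolonging drugs in item 7 are not to be started, in either arm, from the first dose through day 10. If one is clinically needed, the study cardiologist is contacted and study drug is stopped if still being taken.
2. Tell participants to inform any outside prescriber that they may be taking HCQ.
3. Ask about new medicines at the existing calls on days 3, 6 and 10, and record the answers.
4. In sections 1.3 B and 4.7 E, have the stopping rule also require review of any added QT-prolonging drug.

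The cost is a few lines of protocol text, one line in the participant instructions, and one question at three calls (3 × 70 = 210 questions over the trial). The downside is that a few participants may stop study drug early. If the consent form or call scripts already contain steps 2 or 3, only the protocol wording remains to be changed.
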